3.5.1 Rescue Guidelines for Subjects with Protocol-Defined Lack of Glycemic Control

During the double-blind treatment period of the trial, subjects may be eligible for the addition of open label rescue medication (Insulin or other antidiabetic agents except GLP-1 analogs, other DPP4/SGLT2 inhibitors or metformin) to their blinded treatment regimen in order to treat ongoing hyperglycemia.

The sub-sections and table listed below define the lack of glycemic control criteria for initiation of rescue medication and subsequent dose titration of rescue medication.

3.5.1.1 Initiation of Rescue Medication

Pre-specified glycemic criteria (see Table 3.5.1.1), based upon central laboratory FPG and repeat, confirmatory FPG, have been established during the double-blind treatment period, starting at Week 6, and up to Week 24 visits, to determine eligibility for open label rescue medication.

Table 3.5.1.1:	Lack of Glycemic Control Criteria for Initiation of Rescue Medication		
Visit Label		Central Laboratory FPG	
Week 6		FPG > 270 mg/dL (15.0 mmol/L)	
After Week 6 to Week 12 (excluding Week 12)FPG > 240 mg/dL (13.3 mmol/L)		FPG > 240 mg/dL (13.3 mmol/L)	
Week 12 to Week 24 FPG > 200 mg/dL (11.1 mmol/L)		FPG > 200 mg/dL (11.1 mmol/L)	

Subjects with a central laboratory FPG value meeting the lack of glycemic control criterion at a pre-specified visit will be scheduled for a follow-up visit (within 3 - 5 days) to obtain a second central laboratory FPG value and review the subject's glucose meter readings. If the repeat central laboratory FPG value still meets the criterion, the subject must be rescued.

Subjects who meet rescue criteria in the double-blind treatment period must first complete the Rescue Visit procedures before receiving open-label rescue medication to ensure that important trial endpoint measurements are collected. (See Section 5.8.3.1) Following completion of the Rescue Visit, rescued subjects will be given open-label antidiabetic rescue medication (Insulin or other antidiabetic agents except GLP-1 analogs, other DPP4/SGLT2 inhibitors or metformin) to be initiated at the lowest starting dose and titrated in accordance with the approved product label in the applicable country at the discretion of the investigator, in addition to their double-blinded study medication. Rescued subjects will then continue in the double-blind treatment period according to their original visit schedule.

Note: Rescue medication will not be provided by Sponsor in this study.

Following initiation of open-label rescue antidiabetic medication, rescued subjects should be scheduled for titration visits to increase their antidiabetic medication dose, as tolerated and in accordance with the approved product label for that country and by their glycemic response and as per the Investigator's judgment.

3.5.2 Discontinuation Guidelines due to Protocol-Defined Major Hypoglycemia Episode or Recurrent Non-Major Hypoglycemia Episodes

Subjects should not be discontinued from any treatment phase based on single episodes of hypoglycemia or symptoms of hypoglycemia unless clinically indicated. The assessment of a single fingerstick or central laboratory glucose value should not be the sole assessment used to determine subject discontinuation due to hypoglycemia.

Clinical indications for discontinuation due to hypoglycemia may include the following:

- Multiple occasions of episodes outlined below that, in the opinion of the Investigator, indicate that continued treatment with study therapy is not in the best interest of the subject. This includes, but is not limited to:
 - Symptoms suggestive of hypoglycemia (eg, sweating, shakiness, increased heart rate, confusion, dizziness, lightheadedness, or hunger) in the absence of environmental factors known to contribute to hypoglycemia (ie, excess physical activity, concurrent illness, or missed or delayed meal) and/or
 - Documented fingerstick glucose values $\leq 54 \text{ mg/dL}$ ($\leq 3.1 \text{ mmol/L}$).
- A subject may also be discontinued from the study due to severe hypoglycemia as determined by the Investigator.

Down titration of blinded study drug and/or background antihyperglycemic agent will not be allowed at any time during the study.

Saxagliptin and Dapagliflozin	CV181169
and	Clinical Protocol

If fingerstick glucose values are discordant from glycemic control assessed by the central laboratory or with clinical symptoms, the subject's glucose meter should be tested and the procedure for using it reviewed with the subject.

Section 5.3.1.1 provides additional guidance on management and reporting of hypoglycemia.

4 TREATMENTS

All protocol-specified investigational and noninvestigational products are considered study drug.

Saxagliptin and Dapagliflozin and

4.1 **Study Treatments**

Table 4.1: Product Description: Double Blind Treatment Period					
Product Description and Dosage Form	Potency	Primary Packaging (Volume)/ Label Type	Secondary Packaging (Qty) /Label Type	Appearance	Storage Conditions (per label)
Dapagliflozin Tablet	10 mg	HDPE Bottle, 50 count tablets / PNL Double Blind	N/A	Green, plain, diamond shaped, film coated tablet	Store at 15-25 Degrees Celsius (59-77 Degrees Fahrenheit); Store in tightly closed container
Placebo for Dapagliflozin Tablet		HDPE Bottle, 50 count tablets / PNL Double Blind	N/A	Green, plain, diamond shaped, film coated tablet	Store at 15-25 Degrees Celsius (59-77 Degrees Fahrenheit); Store in tightly closed container
Saxagliptin Film Coated Tablet, 5 mg (as the free base)	5 mg	HDPE Bottle, 50 count tablets / PNL Double Blind	N/A	Plain, yellow, biconvex, round, film coated tablet	Store at 15-25 Degrees Celsius (59-77 Degrees Fahrenheit); Store in tightly closed container
Placebo for Saxagliptin Film Coated Tablets		HDPE Bottle, 50 count tablets / PNL Double Blind	N/A	Plain, yellow, biconvex, round, film coated tablet	Store at 15-25 Degrees Celsius (59-77 Degrees Fahrenheit); Store in tightly closed container
Metformin XR (metformin hydrochloride film- coated tablets) manufactured by Bristol- Myers Squibb	500 mg	HDPE Bottle, 100 count tablets / PNL Open Labeled		White to off-white, capsule shaped, biconvex tablets, with "BMS 6063" debossed on one side and "500" debossed across the face of the other side	Store at 20-25 Degrees Celsius (68-77 Degrees Fahrenheit). Dispense in light-resistant containers

Date:

4.1.1 Investigational Product

An investigational product, also known as investigational medicinal product in some regions, is defined as follows:

A pharmaceutical form of an active substance or placebo being tested or used as a reference in a clinical study, including products already with a marketing authorization but used or assembled (formulated or packaged) in a way different from the authorized form, or used for an unauthorized indication, or when used to gain further information about the authorized form.

In this protocol, investigational products (also described in Table 4.1) are: Dapagliflozin 10 mg and matching placebo tablets, saxagliptin 5 mg and matching placebo tablets, and metformin XR 500 mg tablets

4.1.2 Noninvestigational Product

Other medications used as support or escape medication for preventative, diagnostic, or therapeutic reasons, as components of the standard of care for a given diagnosis, may be considered as non-investigational products.

Subjects who require rescue therapy for meeting the FPG rescue criteria shall receive open label insulin or other anti-glycemic medication (with the exception of GLP-1 analogs or other DPP-4/SGLT2 inhibitors or metformin) at the discretion of the investigator. Rescue medication will not be provided by the sponsor.

4.1.3 Handling and Dispensing

The investigational product should be stored in a secure area according to local regulations. It is the responsibility of the investigator to ensure that investigational product is only dispensed to study subjects. The investigational product must be dispensed only from official study sites by authorized personnel according to local regulations.

The investigator should ensure that the investigational product is stored in accordance with the environmental conditions (temperature, light, and humidity) as determined by the sponsor (see Table 4.1). If concerns regarding the quality or appearance of the investigational product arise, do not dispense the investigational product and contact the

sponsor immediately. Please refer to Section 9.2.2 for information on investigational product record retention and Section 4.6 for return and destruction instructions.

Storage facilities for controlled substances must be securely locked and substantially constructed, with restricted access to prevent theft or diversion, as applicable by local regulations.

4.2 Method of Assigning Subject Identification

At the screening visit, each subject will be assigned a unique sequential subject number by the Interactive Voice Response System (IVRS). The subject number will consist of five digits which are assigned sequentially (00001, 00002, 00003, etc.) by the IVRS. This number will be used for identification throughout the study and will not be used for any other participant.

Subjects who meet the criteria will be randomly assigned by IVRS to one of the following three double-blind treatment groups in a 1:1:1 ratio using a centralized blocked randomization schedule ratio into one of the following three blinded treatment arms:

- Saxagliptin 5 mg, dapagliflozin placebo, plus metformin XR
- Dapagliflozin 10 mg, saxagliptin placebo, plus metformin XR
- Saxagliptin 5 mg plus dapagliflozin 10 mg plus metformin XR

Randomization will be stratified by site. Randomization schedules for both subject treatment and containers will be generated and kept by Bristol-Myers Squibb and stored in a secure location with restricted access.

At all study visits when study medication is dispensed, each subject will be assigned a kit number by the IVRS. Kit numbers will be assigned randomly and will correspond to the numbers printed on the packages and kits containing study drug.

Kit numbers will be recorded on the appropriate eCRFs. The IVRS will be available 24 hours per day, 7 days per week.

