8.4.2.1 Primary Efficacy Analysis

The primary efficacy analysis will be performed using a longitudinal repeated measures analysis with terms for baseline value, treatment group, time, the interaction of treatment group and time, and the interaction of baseline value and time, including observations prior to rescue. Point estimates and 95% confidence intervals will be calculated for the adjusted mean changes within each treatment group as well as for the differences in adjusted mean changes between treatment groups.

Sensitivity analyses for HbA1c will include additional repeated measures analyses and analysis of covariance (ANCOVA) analyses. The repeated measures analyses will include two separate analyses including values after rescue, including and excluding a time-dependent covariate for rescue. Two separate ANCOVA analyses of the change from baseline at Week 24 will be performed, with terms for treatment group and baseline value in the model. One analysis will be based on measurements at Week 24 (if prior to rescue, if applicable) or the last post-baseline measurement prior to Week 24 and prior to rescue (if applicable), if no Week 24 assessment is available (ie. last observation carried forward [LOCF]). The second sensitivity analysis using ANCOVA will be based on all subjects completing the short-term double-blind period without requiring glycemic rescue therapy.

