8.4.2.2 Secondary Efficacy Analyses

In order to protect the overall type I error rate, the interpretation of the statistical significance of treatment comparisons for each secondary efficacy endpoint will be done using a step-wise procedure. The secondary endpoints will be tested in the order in which they are listed in Section 8.3.2.

The analysis of the mean change from baseline at week 24 for 2-hour post-prandial glucose during a liquid meal test (2-h MTT) will be based on an ANCOVA model using LOCF methodology with terms for treatment group and baseline value in the model. Analyses of the mean change from baseline at week 24 for FPG, and total body weight will be performed using the same longitudinal repeated measures model as for the primary efficacy endpoint. The analysis of total body weight will compare the saxagliptin 5 mg plus dapagliflozin 10 mg add-on to metformin treatment group versus the saxagliptin 5 mg plus placebo added to metformin group only. Sensitivity analyses for FPG and total body weight will consist of ANCOVA analyses using LOCF methodology.

The proportion of subjects achieving a therapeutic glycemic response (defined as HbA1c < 7.0%) at Week 24 (LOCF) will be summarized by treatment group and compared between treatment groups using the methodology of Zhang, Tsiatis, and Davidian⁶ and Tsiatis, Davidian, Zhang, and Lu⁷ 95% confidence intervals for the response rate within each treatment group as well as for the difference in response rates between treatment groups will be calculated with adjustment for baseline HbA1c.

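### Randomization is stratified by site, but no specified efficacy model contains site or a grouping of sites, so the tests are mildly conservative to the extent that sites differ

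*Protocol*

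**What the plan says.** Protocol Section 4.2 allocates subjects "in a 1:1:1 ratio using a centralized blocked randomization schedule" and adds: "Randomization will be stratified by site". It gives neither block size nor number of sites.

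The analysis sections list their model terms explicitly:

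- **Primary HbA1c analysis (8.4.2.1):** repeated measures "with terms for baseline value, treatment group, time, the interaction of treatment group and time, and the interaction of baseline value and time".
- **HbA1c sensitivity ANCOVAs (8.4.2.1):** these "will be performed, with terms for treatment group and baseline value in the model".
- **2-hour post-meal glucose (8.4.2.2):** an "ANCOVA model using LOCF methodology with terms for treatment group and baseline value in the model".
- **FPG and body weight (8.4.2.2):** "the same longitudinal repeated measures model as for the primary efficacy endpoint".
- **HbA1c responders (8.4.2.2):** adjusted for baseline HbA1c only.
- **MTT AUC endpoints and lipids (8.4.2.3):** the AUCs use the primary model. The lipid model has treatment, time and log-baseline terms.

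None of these includes site or a grouping of sites. Geographic region appears only among the baseline characteristics to be summarized (8.4.1). The Synopsis repeats the primary model without site.

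**The concern.** Blocked allocation within site makes the arms nearly equal at each site, so site differences largely cancel from the treatment contrast. A model without site does not use that fact. It leaves between-site variation in the residual, and the reported standard error is larger than the true sampling error of the estimate. Confidence intervals are then somewhat wide, and p-values somewhat large.

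This applies to both comparisons of the min test, each of which must reach two-sided 0.05 (8.1), and again at each step of the ordered secondary testing (8.4.2.2). Because the protocol fixes the model terms itself, an analysis plan that follows it would carry the omission forward. A site adjustment chosen after unblinding would be open to challenge.

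**Working it through.** **Inputs from Section 8.1.** Difference 0.4%, SD 1.0%, 163 per arm, two-sided 0.05 for each comparison, both required; 5% without a post-baseline value.

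**Inputs not in the protocol.** The share ρ of residual HbA1c-change variance lying between sites, the number of sites and the block size. These are assumed below.

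**1. The protocol's sample size reproduces.** For 95% power per comparison, n = 2 × (1.960 + 1.645)² × 1.0² / 0.4² = 162.4, so 163. The standardized difference is 0.4 / √(2/163) = 3.611, and power per comparison is Φ(3.611 − 1.960) = 0.951. Joint power is at least 2 × 0.951 − 1 ≈ 0.90. With the correlation of 0.5 that comes from the shared combination arm, it is 0.913. Then 163 / 0.95 = 171.6, so 172 per arm and 3 × 172 = 516. Site plays no part in this calculation.

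**2. Effect of omitting site, under perfect within-site balance.** Hold the total residual SD at 1.0 and let f = √(1 − ρ).

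- Reported standard error divided by true standard error: 1/f
- Actual two-sided level: 2 × (1 − Φ(1.960/f))
- Power per comparison without site: Φ((3.611 − 1.960)/f)
- Power per comparison with site modelled: Φ(3.611/f − 1.960)
- Joint power: bivariate normal, correlation 0.5

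| ρ (assumed) | SE overstated by | Actual level | Joint power, no site | Joint power, site modelled | Forgone (points) |
|---|---|---|---|---|---|
| 0 | 0% | 0.050 | 91.3% | 91.3% | 0 |
| 2% | 1.0% | 0.048 | 91.6% | 91.9% | 0.3 |
| 5% | 2.6% | 0.044 | 92.0% | 92.8% | 0.8 |
| 10% | 5.4% | 0.039 | 92.7% | 94.2% | 1.4 |

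**3. The same effect in subjects, at ρ = 5%.** Here f = 0.9747 and 1.960 × (1 − f) = 0.0496. With site modelled, matching the power of the unadjusted test at 163 needs n = 2 × ((3.611 − 0.0496)/0.4)² = 158.6 per arm. Conversely, the unadjusted test needs n = 2 × ((3.611 + 0.0496)/0.4)² = 167.5 to match the adjusted test at 163. The difference is about 4.5 per arm either way.

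**4. Does the form of adjustment matter?** Perfect balance is an idealization, so the comparison was also simulated with 489 subjects, unequal site sizes, blocks of 3 and a single time point. Joint power:

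| Sites | ρ | Fixed effect per site: without / with | Random site intercept: without / with |
|---|---|---|---|
| 50 | 0 | 91.6 / 91.2% | 91.3 / 91.4% |
| 50 | 5% | 91.3 / 91.8% | 91.8 / 92.5% |
| 150 | 0 | 90.7 / 86.8% | 90.7 / 90.9% |
| 150 | 5% | 91.9 / 89.9% | 91.5 / 92.3% |

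The two pairs of columns come from separate simulations (5,000 and 8,000 runs per case), so their "without" values differ by chance. With the random intercept the level was 0.048 to 0.050 throughout. A fixed effect for every site loses power when there are many small sites; the random intercept did not lose power in any case run.

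**The case against.** Leaving the stratification factor out is a choice about efficiency, not an error of validity. The treatment contrast is unbiased and the level is at or below 0.05. Joint power without site is 91.3% to 92.7% over the assumed range, above the 90% promised. If the SD of 1.0% already includes between-site variation, the sample size covers it. HbA1c is measured centrally and the primary analysis uses only values before rescue, so the between-site share may well be small. All of this stands.

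Three stronger readings are tempting, and the protocol does not support them:

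- **That the primary test is conservative as a matter of fact.** It is so only if sites differ after baseline adjustment. At ρ = 0 the level is exactly nominal, and the protocol gives no value for ρ.
- **That the precision gained by stratifying is lost.** Balance still lowers the true variance of the estimate, which is why power without site rises with ρ in the table. Only the reported standard error is too large.
- **That a 5% share is worth ρ × n = 0.05 × 163 ≈ 8 subjects per arm.** Solving for equal power gives about 4.5, because the unadjusted test already benefits from the balance.

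The objection does not justify leaving the point unaddressed. The protocol stratifies by a factor, lists its model terms, omits that factor and does not say why.

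**Conclusion.** The mismatch between design and analysis is plain in the text. Its effect is small and in the safe direction: standard errors overstated by 0% to 5.4%, an actual level between 0.050 and 0.039, and at most about 1.4 points of joint power forgone, for between-site shares of 0% to 10%. Neither validity nor the planned 90% power is threatened.

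The sizes rest on an assumed ρ, on perfect within-site balance and on a total residual SD of 1.0%. Incomplete blocks at small sites would reduce the effect. The simulations use one time point, so they indicate rather than measure what a site intercept would do in the repeated-measures model. This is a modest point of efficiency and consistency, worth settling because it is cheap to settle before unblinding.

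**What to change.** Add the stratification factor to the repeated-measures and ANCOVA models in Section 8.4.2. Either of two forms will do:

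- site as a random intercept; or
- pooled sites, or geographic region (already collected for the baseline table), as a fixed effect, with the pooling rule for small sites written down before unblinding.

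Use the pooled factor as an added covariate in the responder analysis. Do not fit a separate fixed effect for every site. If the sponsor prefers to keep the present models, Section 8.4.2 should say why the stratification factor is left out.

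The cost is small: one model term, a pooling rule, a matching change to the responder analysis and slightly more modelling work. Pooling by region removes only the variation between regions, so it recovers less than a site-level term. Sample size, visits and data collection do not change.

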4.3 Selection and Timing of Dose for Each Subject

Blinded Study Medication

Saxagliptin 5 mg tablets and matching placebo tablets, administered orally once daily for the 24-week double-blind treatment period. Saxagliptin 5 mg is the maximum

recommend daily dose as well as the usual daily dose. It is not currently labeled for triple therapy use in combination with dapagliflozin and metformin.

Dapagliflozin 10 mg tablets and matching placebo tablets administered orally once daily for the 24-week double-blind treatment period.

Dapagliflozin 10 mg is an investigational drug. Based on considerations of efficacy, pharmacodynamic, and safety data from the Phase 1 and 2 programs, daily doses up to 10mg of dapagliflozin have been chosen for the Phase 3 studies. The 10 mg dose was chosen for this study as it has been extensively studied in Phase 3 trials and is the dose expected to deliver the most favorable benefit:risk profile.

Open Label Metformin

Subjects entering the study on metformin IR will be switched to open-label metformin XR 500 mg tablets administered orally once daily with food at doses \geq 1500 mg/day from the 4-week lead-in period. Subjects whose current therapy is not based on 500 mg metformin IR tablets will have their dose modified as noted in Appendix 4 and for the 24-week double-blind treatment period.

Subjects entering the study on metformin XR, whose current therapy is not based on 500 mg metformin XR tablets, will have their dose modified as noted in Appendix 4 for the lead-in period and for the 24-week double-blind treatment period.

Subjects must be receiving metformin in accordance with the product label for their country.

4.4 Blinding/Unblinding

Blinding is critical to the integrity of this clinical study. However, in the event of a medical emergency or pregnancy in an individual subject, **in which knowledge of the investigational product is critical to the subject's management**, the blind for that subject may be broken by the treating physician.

Before breaking the blind of an individual subject's treatment, the investigator should have determined that the information is necessary, ie, that it will alter the subject's immediate management. In many cases, particularly when the emergency is clearly not investigational product-related, the problem may be properly managed by assuming that the subject is receiving active product without the need for unblinding.

Saxagliptin and Dapagliflozin	CV181169
and	Clinical Protocol

In cases of accidental unblinding, contact the Medical Monitor and ensure every attempt to preserve the blind is made.

4.5 Treatment Compliance

Each time study medication is dispensed, compliance will be reinforced. When study medication is returned, compliance will be assessed based upon subject's interview and a count of the tablets returned. Compliance should be between $\geq 80\%$ and $\leq 120\%$. The Investigator (or designee) will record the amounts of study medication dispensed and returned at each visit, as well as document reasons for non-compliance, in the source document. The dates of all study medication dosing, including interruptions, missed doses or overdose, must be recorded on the eCRF. If the subject is not > 80% compliant with recording study drug doses during the study the period of non compliance should be noted as a protocol deviation and the sponsor should be notified. The subject should be educated regarding recording these values.

